7.1.5 Phone Visit 2: Safety Check (Week 6)

• Study staff phone call to address AEs/SAEs

7.2 Early Withdrawal

If subject withdraws from the study after the screening visit, but before visit 2, no further evaluations are necessary. If subject withdraws from the study after visit 2, all safety assessments will be performed (see section 7.3).

7.3 Safety

For all safety assessments described below, any clinically significant change will be recorded as an AE or SAE.

7.3.1 Physical Examination

Complete physical examination will be performed at visits, 1 and 3, or if the subject withdraws or is withdrawn from the study early. Any abnormalities noted at Visit 1, will be documented as part of the subject's medical history.

7.3.2 Neurological Examination

Neurological examination will be performed at visits 1, 3 or if the subject withdraws early. Any abnormalities noted at Visit 1, will be documented as part of the subject's medical history.

7.3.3 Vital Signs

Vital signs will be recorded at all visits. For within subject consistency, brachial artery pressure will be obtained in the routine fashion.

Blood pressure and heart rate to be measured after subject has been sitting quietly for a minimum of 5 minutes. Diastolic blood pressure will be measured at the disappearance of Korotkoff sounds. Vitals sign will be monitored by clinical staff during each visit of the study.

A blood glucose < 70 mg/dL will be considered clinically significant. Subjects will be given training regarding hypoglycemic rescue therapy and contacting 911 in severe cases. Any episodes will be reported to the study coordinator and research team. The likelihood of peripheral hypoglycemia is relatively low based on numerous clinical trials performed in the AD and healthy aging population showing no effects of IN insulin on peripheral glucose.

Vital signs will be taken prior to ECG and blood draw.

7.3.4 Weight

Body weight will be measured at all visits.

7.3.5 ECG

A standard 12-lead ECG will be performed on subjects at visit 1.

7.3.6 Laboratory Samples

All subjects will be required to fast for a minimum of 12 hours prior to collection of blood sampling.

See Table 1 for a specific list of laboratory assessments.

Table 1: Schedule of Assessments

Assessment/ Procedure	Visit 1: Screen	Visit 2: Baseline/Initial Treatment	Phone Visit 1: Safety Check	Visit 3: Final Treatment / Safety	Phone Visit 2: Safety Check	Early Withdrawal
			A		2	
Schedule - Week and Windows	- 2	0	2	4	6	
		± 5 days	± 3 days	± 5 days	± 3 days	
Informed consent	Х					
Review of inclusion/exclusion	Х	Х				
criteria						
Medical History, demographic	Х					
Physical/neurological exam	Х			х		Х
Vital signs	Х	Х		Х		Х
Height	Х					
Weight	Х	Х		х		Х
12-lead ECG	Х					
Basic Metabolic Panel (Na, K,	Х			х		Х
CO2, CL, BUN, Creatinine, Glucose						
and Ca)						
Insulin Level	Х			Х		
HbA1c	Х					
Thyroid Stimulating Hormone	Х					
(TSH)						
Vitamin B12	Х					
Pregnancy Test (in females)	Х					
EXAMINER BATTERY		Х		х		
MMSE	Х					
APEHQ		Х		х		
C-SSRS		Х		Х		Х
Study Drug administration training	Х	Х				
Hypoglycemia rescue training	Х	Х				
Glucose finger sticks (baseline		Х				
before 1 st dose; 15 & 30 minutes						
after 1 st dose)						
Concomitant mediations		Х		х		
IN INSULIN compliance			х			
Adverse events		Х	х	х	х	х

7.4 Neuropsychological Assessment

See Table 1 for a specific list of neuropsychological assessments

7.4.1 EXAMINER BATTERY

The EXAMINER battery was developed at the University of California, San Francisco Memory and Aging Center as a means of validly assessing domains of executive function in an assortment of ages and disorders to capture real-life social and executive deficits in subjects with frontal lobe disorders (http://www.memory.ucsf.edu). The battery consists of subtests in a variety of domains that include working memory, inhibition, set-shifting, fluency, planning, insight, and social cognition/behavior.

7.4.1.1 Working Memory Subtests:

7.4.1.1.1 Dot Counting:

The dot counting task measures verbal working memory. The examinee is asked to look at a screen with a mixed array of green circles, blue circles and blue squares. The examinee is asked to count all of the blue circles on the screen one at a time, out loud and remember the final total. Once the examinee finishes counting the blue circles on one screen, the examiner switches the display to a different mixed array of green circles, blue circles and blue squares. The examinee is instructed to count the blue circles in the new display. The number of different displays presented to the examinee in each trial increases from two to seven over six experimental trials. After counting the blue circles on all of the displays presented within a trial, the examinee is asked to recall the total number of blue circles that were counted in each of the different displays in the order in which they were presented. Partial credit is given based on how many totals the examinee can recall correctly from each trial.

7.4.1.1.2 N-Back

The n-back paradigm is a widely used measure of working memory that requires flexible updating capabilities. EXAMINER includes a spatial 1-back and 2-back task to assess spatial working memory. The 1-back requires maintaining and updating 1 location at a time, whereas the more difficult 2-back requires maintaining and updating 2 locations.

7.4.1.2 Inhibition

7.4.1.2.1 Flanker

A row of five arrows is presented in the center of the screen. The examinee is required to indicate whether the centrally presented arrow is pointing either to the left or right by pressing the left or right arrow key. The examinee is presented with two different conditions during the task, incongruent and congruent. In the congruent trials, the non-target arrows point in the same direction as the target arrow and in the incongruent trials they point in the opposite direction. Examinees should respond as quickly and accurately as possible.

7.4.1.2.2 Continuous Performance Task

The continuous performance task is a classic response inhibition task, which requires subjects to respond to a certain type of stimulus and withhold a response to another.

7.4.1.2.3 Anti-saccades

The subjects look at a fixation point in the center of a computer screen and move their eyes upon presentation of a laterally presented stimulus. In the first block (pro-saccade), subjects are instructed to move their eyes in the direction of the presented stimulus. In the second and third blocks (anti-saccade), subjects are instructed to move their eyes in the opposite direction of the presented stimulus.

7.4.1.2.4 Dysexecutive Errors

An underlying assumption in developing the EXAMINER battery is that executive related deficits can manifest as impulsive errors, failure to shift set, perseverative behavior, and stimulus-boundedness, even when achievement scores on tests are unremarkable. Accordingly, we generated a composite error score using false responses and rule violations on a variety of EXAMINER tasks, including: CPT, verbal fluency tasks, Flanker, and Set Shifting.

7.4.1.3 Set-Shifting

Subjects are required to match a stimulus on the top of the screen to one of two stimuli in the lower corners of the screen. In task-homogeneous blocks, subjects perform either Task A (e.g., classifying shapes) or Task B (e.g., classifying colors). In task-heterogeneous blocks, subjects alternate between the two tasks pseudo-randomly. The combination of task-homogeneous and task-heterogeneous blocks allows measurement of general switch costs (latency differences between heterogeneous and homogeneous blocks) and specific switch costs (differences between switch and non-switch trials within the heterogeneous block).

7.4.1.4 Fluency

7.4.1.4.1 Phonemic Fluency

For the phonemic fluency task, examinees are instructed to name as many words as they can that begin with a particular letter of the alphabet as quickly as they can. Sixty seconds are allowed for each letter.

7.4.1.4.2 Categorical Fluency

For the category fluency task, examinees are asked to generate as many items that they can think of that belong to a particular category as quickly as possible. Sixty seconds are allowed for each category.

7.4.1.5 Planning

7.4.1.5.1 Unstructured Task

This task was modeled after the 6-elements test (Shallice and Burgess, 1991). Subjects are presented with three booklets, each containing five pages of simple puzzles (4 per page). The puzzles were designed to be cognitively simple (e.g., connect the dots; trace the design) but average completion times range from 4 to 60 seconds. Each puzzle has a designated point value, and subjects are given 6 minutes to earn as many points as possible. Irrespective of actual point value, puzzles can have a high cost-benefit ratio (i.e., the time required to complete the puzzle makes it less desirable) or a low cost-benefit ratio (i.e., the time required to complete the puzzle makes it more desirable). In addition, the proportion of low cost-benefit items decreases as subjects proceed through a booklet. Subjects need to plan ahead, avoid items that are strategically poor choices, and be cognizant of when a particular booklet offers diminishing returns.

7.4.1.6 Insight

Examinees are asked to rate themselves on their performance immediately after completing the wellnormed verbal fluency tasks. They are instructed to assess their own performance relative to a hypothetical sample of 100 people of a similar age and level of education.

7.4.1.7 Social Cognition and Behavior

7.4.1.7.1 Social Norms Questionnaire

This task measures subjects' crystallized knowledge of social norms in a linguistically and cognitively simple manner. This yes-no questionnaire is designed to determine the degree to which subjects actually understand and can accurately identify implicit but widely accepted social boundaries in the dominant U.S. culture. The Social Norms Questionnaire includes both socially inappropriate behaviors (e.g., "Cut in line if you are in a hurry," "Pick your nose in public,") and generally acceptable behaviors (e.g., "Tell a coworker your age"). The subject must decide whether the behavior is socially appropriate or not if it were hypothetically enacted with an acquaintance or coworker.

7.4.1.7.2 Behavioral Rating Scale

This rating scale is completed by the examiner after completion of the testing. Examiners restrict their ratings to behaviors that they have observed directly, but include all observed behaviors, regardless of the context. Thus, although behaviors during the actual assessment will likely provide the bulk of data, examiners should also note behaviors exhibited in all other situations, such as the waiting room and walking to and from the exam room. There are nine behavioral domains to rate, including agitation, stimulus-boundedness, perseverations, decreased initiation, motor stereotypies, distractibility, degree of social/emotional engagement, impulsivity, and social appropriateness.

7.4.2 Appetite and Eating Habit Questionnaire (APEHQ)

The APEHQ consists of 34 questions that examine changes in eating behaviors in the following domains: swallowing, appetite, eating habits (stereotypic eating behavior and table manners), food preference (including sweet preference and other food fads), and other oral behaviors (eg, food cramming, increased smoking). Caregivers are asked to rate the frequency (0 = never, 1 = less than weekly, 2 = about once a week, 3 = several times a week, 4 = daily or continuously) and severity (0 = N/A [not applicable], 1 = mild, 2 = moderate, and 3 = marked) for each behavior. A composite score of frequency × severity is calculated for each question, and an overall score derived for each domain (Ahmed et al., 2014a).

7.4.3 Columbia-Suicide Severity Scale 0 (C-SSRS)

The Columbia–Suicide Severity Rating Scale (C-SSRS) was designed to quantify the severity of suicidal ideation and behavior (Posner K, 2011). In this study, suicidal ideation and behavior will be prospectively assessed using the C-SSRS. The C-SSRS will be administered by trained raters at specified time points, as indicated in table 1 as well as when clinically indicated. Any subjects demonstrating evidence of suicidality will prompt immediate consultation with the site's on-call psychiatrist for assistance with decision-making and potential referral to behavioral health services.

8 Investigational Product(s)

8.1 Description of Investigational Product

The Center for Memory & Aging will utilize the following investigational products:

- Intranasal delivery route
- Regular insulin [(Novolin-R); see section15.3]
- Aerosol nasal device(Sections 2, 5.2, 5.3, 15.2 and Investigator's brochure- 15.1)

8.2 Handling and Storage

The study drug (insulin) will be given to subject/care partner after training for administration at visit 2.

Subjects will be instructed to keep study drug at room temperature according to label recommendations.

The study drug will be kept at study site per label recommendations and institutional Standard Operational Policy. To ensure that a stable temperature and/or conditions are maintained, site staff will verify and document refrigerator/room temperature at a minimum of three times per week or monitored continuously if automated systems such as temp trak are used. A log will be securely stored NIFT-D

at the HealthPartners Center for Memory & Aging. Study staff will be responsible for safeguarding and maintaining the master log.

8.3 Packaging and Labeling

All study drug will be labeled according to the following specifications:

- Protocol identifier/IRB study number
- Quantity statement
- Subject ID #
- "For Clinical Trial Use Only"
- Study contact # [contact]

8.4 Occupational Safety

No known significant safety risks exist to site personnel in direct or indirect contact with the study drug.

9 Concomitant Medications and Non-Drug Therapies

9.1 Permitted Medications

Any medication not listed in list of Prohibited Medications (Table 2) will be permitted during this study. A record will be kept by site staff detailing doses and indication of any concomitant medications used by subjects.

9.2 Prohibited Medications

Subjects taking prohibited medications at time of screening will not be allowed to participate in study, unless such treatment is discontinued at least 30 days prior to screening. These medications include anticholinergics, and centrally acting antihistamines (e.g. Benadryl), opiates, benzodiazepines, barbiturates, muscle relaxants, and insulin. Randomized subjects taking a prohibited medication (episodic or PRN) will be considered for study participation on an individual basis.

Table 2: Prohibited Medications

Anticholinergics
Antihistamines (centrally-acting)
Barbiturates
Benzodiazepines
Insulin
Muscle relaxants
Opioids

10 Subject Completion and Withdrawal

10.1 Subject Completion

Subjects completing all 5 study visits (including the 2 phone visits) will be considered to have completed study.

10.2 Subject Withdrawal

Subject may withdraw from study at any time for any reason without penalty or be terminated from the study by the clinical investigator (see provisions for termination by study team.) Investigational team will document the reason(s) for withdrawal. In the event a subject chooses to withdraw from study before Visit 3, the safety procedures described in Section 7.3 will be performed ideally within 3 days following subject's decision to withdraw. For all subjects who withdraw, all final safety assessments will be collected regardless of time elapsed since previous visit. In addition to the termination visit, subjects who withdraw early will be contacted within 7 days by study staff via telephone to assess development of new and/or ongoing AEs and concomitant medications. Efforts will be made to recruit subjects to replace any withdrawals at any point so as to maintain an n=12.

Subject's participation may be terminated at the discretion of the investigator. Individuals may be withdrawn for the following reasons:

- Clinically significant adverse events
- Lost to follow-up
- Protocol violations
- Inability to tolerate study medication
- Other

11 Adverse Events (AE) and Serious Adverse Events (SAE)

11.1 Definition of AE

An adverse event is any symptom, sign, illness or experience which develops or worsens in severity during the course of the study. Intercurrent illnesses or injuries should be regarded as adverse events. Abnormal results of diagnostic procedures are considered to be adverse events if the abnormality:

- Results in study withdrawal
- Is associated with clinical signs or symptoms
- Leads to treatment or to further diagnostic tests
- Is considered by the investigator to be of clinical significance

11.2 Definition of SAE

Adverse events are classified as either serious or non-serious. A serious adverse event is any event that results in:

- Death
- Life-threatening situation
- Hospitalization or prolongation of hospitalization
- Disability or incapacitation

• Other events determined by investigator to be medically significant in which subject's well-being is jeopardized (e.g. events that have high likelihood of escalating to the point of meeting criteria outlined above)

11.2.1 Clinical Laboratory Abnormalities & Other Abnormal Assessments as AEs & SAEs

Any new abnormal, vital, examination, or laboratory finding judged clinically significant by the investigator will be documented as an AE or SAE, if meeting the definitions for such. Abnormal lab findings or other abnormal assessments associated with the disease under study will not be considered AEs or SAEs unless more severe than expected, as judged by the investigator.

11.2.2 Time Period and Frequency of Detecting AEs and SAEs

Upon consenting, a subject is considered to be a subject in the study, and until that person either withdraws or completes study, AEs and SAEs will be recorded. The investigational team will promptly report any AE/SAE as required per federal guidelines.

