3.1 Primary Objective

- Evaluate the feasibility of using the EXAMINER battery as a cognitive outcome measure in frontotemporal dementia (FTD)
- Evaluate the HealthPartners Center for Memory & Aging's recruitment capacity for FTD subjects Assess the safety and tolerability of intranasal (IN) insulin in FTD subjects

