4.1 Primary Endpoints

- Number of subjects completing the EXAMINER battery
- Number of subjects enrolled
- Total number of AEs and SAEs

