4.2 Secondary Endpoints

- Reasons for subjects failing to complete EXAMINER battery
- Number of subjects completing the study
- Number of screen failures
- Reasons for screen failure
- Number of unique subjects with an AE/SAE

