4.4 Safety

- Incidence and severity of serious adverse events (SAEs) and adverse events (AEs)
- Frequency of change in clinically-significant vital signs, physical exam or neurological exam
- Plasma glucose level <70mg/dl

5 Study Design

This study is a single center trial of intranasal (IN) regular insulin in subjects with probable behavioral variant FTD (bv-FTD) and semantic variant PPA (sv-PPA) and is designed to assess –

- 1) Evaluate the feasibility of using the EXAMINER battery as a cognitive outcome measure in frontotemporal dementia (FTD),
- 2) Evaluate the HealthPartners Center for Memory & Aging's recruitment capacity for FTD subjects and
- 3) Assess the safety and tolerability of intranasal (IN) insulin in FTD subjects.

After written informed consent has been obtained from the subject and family member/caregiver, subjects will be screened to assess study eligibility based on study inclusion/exclusion criteria. Subjects who are eligible at the end of the screening visit (Visit 1) will be scheduled for a baseline to take place 2 weeks later (Visit 2). During the baseline visit, subjects will be administered the EXAMINER battery and APEHQ questionnaire. A final safety/assessment visit will take place four weeks after visit 2 (Visit 3) at which time the EXAMINER battery and APEHQ questionnaire will be re-administered. There will be two phone visits (one between visit 2 and 3 and another after visit 3) to address study drug compliance and AEs/SAEs.

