12.2 Statistical Analysis of Primary Outcomes

To evaluate the feasibility of using the EXAMINER battery as a cognitive outcome measure in the FTD population, we will report the number and percentage of our sample who were able to complete the battery. We will also document any reasons for incomplete data. We will then describe any factors that affect implementation ease or difficulty including battery components that were more challenging for subjects with advanced FTD. Finally, we will discuss the speed and efficiency of administering the tool.

The Center for Memory & Aging's recruitment capacity will be assessed by reporting the number and percentage of subjects who were: 1. contacted for participation, 2. screened, 3. screened positive, 4. able to complete the study. We will also report the average number of visits attended by our sample and any reason for screen failure or early withdrawal.

The number of unique subjects who experienced an adverse event or serious adverse event as well as the total number of each will be reported. A brief written description of these events will be provided. Suicidality, as assessed by the C-SSRS, will be included as an adverse event.

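### The primary AE/SAE total runs from consent with no dosed safety set, named denominator or split at first dose, so pre-dose events can enter the insulin safety count

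*Combined protocol and SAP*

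**What the plan says.** Section 3.1 includes the objective "Assess the safety and tolerability of intranasal (IN) insulin in FTD subjects". The matching primary endpoint in 4.1 is "Total number of AEs and SAEs", and 4.2 adds the secondary endpoint "Number of unique subjects with an AE/SAE". Section 4.4 also lists "Incidence and severity of serious adverse events (SAEs) and adverse events (AEs").

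Recording begins at consent (11.2.2): "Upon consenting, a subject is considered to be a subject in the study, and until that person either withdraws or completes study". The AE definition in 11.1 is tied to the study and not to treatment: "any symptom, sign, illness or experience which develops or worsens in severity during the course of the study". Consent is taken at Visit 1 (Week -2, section 7.1.1), and the first dose is given at Visit 2 (Week 0, section 7.1.2).

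The planned analysis in 12.2 is "The number of unique subjects who experienced an adverse event or serious adverse event as well as the total number of each", followed by "A brief written description of these events will be provided". The same section counts suicidality found on the C-SSRS as an adverse event. The only rule on who is included in an analysis, in 12.1, concerns the EXAMINER and APEHQ scores.

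**The concern.** The trial has no control arm. Two facts do most of the work in reading an AE count as evidence about insulin: whether the event began before or after the first dose, and how many people were dosed. The plan asks for neither in the analysis. A total that starts at consent can include events that precede any exposure. A count of affected subjects with no named denominator leaves it open whether the incidence in 4.4 refers to those consented, enrolled or dosed.

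This goes beyond missing detail. Followed literally, the stated rules produce the pooling: they set the start at consent, place AE collection at Visit 2, and ask for one total. The result would be a primary endpoint that does not quite measure the objective it serves.

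**Working it through.** **The plan's own figures.** The plan gives no figure for the AE endpoint. Its one statistical figure, the ±22.6% in 12.4, reproduces as 1.96 × √(0.8 × 0.2 / 12) = 0.226. It concerns EXAMINER completion and has no bearing here.

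**Share of the recording period before first dose.** Inputs from Table 1 and sections 7.1.1 to 7.1.5: screening at Week -2, first dose at Week 0, final visit at Week 4, last phone call at Week 6.
- Pre-dose: 14 days. Post-dose: 42 days.
- Share = 14 / (14 + 42) = 14/56 = 25%. For 12 completers: 12 × 14 = 168 of 12 × 56 = 672 subject-days.
- Section 5.5 gives about 9 weeks of participation where the schedule gives 8. With the pre-dose interval held at 14 days, the share is 14/63 = 22%.
- With Visit 2 at 14 ± 5 days and 42 days after dosing: 9/51 = 18% to 19/61 = 31%.

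These are shares of scheduled time. The documents give no AE rate, and detection differs across the period, so the share of events cannot be computed.

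**How a pre-dose event would enter the count.**
- Table 1 and 7.1.2 schedule AE collection at Visit 2, which covers the interval since screening.
- The C-SSRS is first given at Visit 2 and not at screening. Section 7.1.2 lists it ahead of the first dose, and 12.2 counts suicidality as an AE with no exception for baseline findings. If the listed order is the order followed, ideation present before any insulin would be counted.
- A fingerstick is taken before the first dose. Section 4.4 lists glucose below 70 mg/dl as a safety endpoint with no time anchor.

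**Denominator.** Targeted Accrual in the Protocol Summary plans 20 consented for 12 subjects. Eligibility is reviewed again at Visit 2, and 10.2 replaces withdrawals, so the number dosed may differ from both 12 and 20. Section 12.2 will report the numbers contacted, screened, screened positive and completing. The number dosed lies between completers and those screened positive, but it is not itself a planned output.

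**Direction.** Pooled total = pre-dose events + post-dose events. The first term cannot be negative, so the pooled total is never below the post-dose count.

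**End of the period.** Section 11.2.2 stops recording at withdrawal. Section 10.2 requires a call within 7 days to ask early withdrawals about new or ongoing AEs. The plan does not say whether events found on that call are counted.

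**The case against.** The strongest reply is that this is a small descriptive pilot in which a reader will see most of the timing anyway. AEs are collected at Visit 2, then separately at Week 2, Visit 3 and Week 6, so there is a contact at the first-dose boundary, and 12.2 promises a written description. That is fair, but nothing requires the description to give onset relative to dosing, and the headline endpoint stays pooled.

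Recording from consent is also sound practice. That stands, and only the analysis needs to change.

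Three stronger readings are tempting and are not supported:
- A reader might infer that incidence cannot be calculated. The primary endpoint is a count and needs no denominator, and the number dosed should be largely recoverable from the disposition figures. The fair charge is that the denominator is not named.
- A reader might infer that a quarter of the reported events will be pre-dose. The 25% is calendar time only.
- A reader might infer that the 20 - 12 = 8 extra consented subjects will swell the total. Section 7.2 requires no further evaluation of anyone who withdraws before Visit 2, Table 1 has no AE entry at Visit 1, and abnormalities on the Visit 1 examinations go to medical history (7.3.1, 7.3.2). Never-dosed subjects will probably add few events.

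On the end of the period, one can read the specific instruction in 10.2 as governing, and Table 1 does mark AEs under Early Withdrawal. That resolves most of the conflict, which is a separate and smaller point.

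**Conclusion.** The point holds as a defect of definition and reporting. As written, the plan pools events from before and after the first dose into a primary endpoint meant to describe insulin safety, and it names no dosed set or denominator. About 25% of scheduled time per completer is pre-dose, assuming visits on their nominal dates. The number of events affected is unknown.

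The consequence is limited. Pooling cannot conceal an on-treatment event within the total; it can only add to it. The feasibility rule in 12.4 rests on EXAMINER completion and on recruiting 12 subjects, and no test or threshold in the plan uses the AE count. A reader might conclude that the safety result would be invalid, but the documents do not support that. This is an inexpensive improvement that should be made before results are seen.

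**What to change.** Leave recording from consent unchanged.

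1. In 12.2, define the safety set as subjects given at least one dose, and use its size as the denominator for the subject count and for the incidence in 4.4.
2. Report AE and SAE counts split at first dose. Use events with onset or worsening from first dose to the last safety contact as the count for insulin safety.
3. List pre-dose events, and any events in never-dosed subjects, separately. State in 12.2 that C-SSRS findings made before the first dose belong in this list.
4. Align the endpoint wording in the Protocol Summary, 4.1 and 4.2.
5. Reconcile 11.2.2 with 10.2 so that events found on the post-withdrawal call are counted.

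The cost is a short amendment, a slightly smaller headline count, and an onset date or before/after-dose flag on the AE form if it lacks one. The forms are built by the site (13.7) and are not in the documents. No visit or procedure is added.
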